**9.2.3. SAS Code for the Confidence Interval for Risk Difference using Chan and Zhang (1999)**

```
PROC BINOMIAL DATA=<DATASET> GAMMA=0 ALPHA=<Value>;

PD/EX ONE STD;

PO <POPULATION VARIABLE>;

OU <OUTCOME VARIABLE>;

RUN;
```

**9.2.4. SAS code for the Confidence Interval of a Binomial Proportion (Blyth-Still-Casella)**

```
PROC BINOMIAL DATA=<DATASET> ALPHA=<value>;

BI/BS;

OU <RESPONSE VARIABLE>;

RUN;
```

**9.3. Assignment of Observations to the Visits**

Visit window (applicable for efficacy and PRO endpoints) will be assigned to the subjects in the Psoriasis cohorts. The observations that are observed within the time window of ( $\pm 3$  days) around the target date will be assigned to the visit with the corresponding target date. The resulting assignment of observations to the post-baseline and baseline visits is shown in the following table.

**Definition and Use of Visit Windows in Reporting**

Visit Label	Targeted Day	Analysis Window
Screening	28 days prior to Day 1	1-30 days prior to Day 1
Baseline*	Day 1 (reference day)	Day 1 (reference day)
Week 1	Day 7	Days 4-10
Week 2	Day 14	Days 11-17
Week 3	Day 21	Days 18-24
Week 4	Day 28	Days 25-31
Week 5	Day 35	Days 32-38
Week 6	Day 42	Day 39-45
Week 8	Day 56	Day 53-59
Week 12	Day 84	Day 81-87

\*In case Day 1 measurement is missing, the last available pre-dose will be considered as the baseline

If more than one observation from the same subject falls into the same window then the association of the observation with the visit will be done after the consultation with the study clinician and lead statistician.

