### **5.2. Breaking the Blind**

This study will be subject and investigator blinded, sponsor-open. At the initiation of the study, the study site will be instructed on the method for breaking the blind. The method will be manual. Blinding codes should only be broken in emergency situations for reasons of subject safety. Whenever possible, the investigator or sub investigator should consult with a member of the study team prior to breaking the blind. When the blinding code is broken, the reason must be fully documented and entered on the case report form.

Blood specimens will be obtained from all subjects for pharmacokinetic analysis to maintain the study blind at the investigator site. For the SAD/MAD cohorts only the investigator site(s) and the study monitor(s) will be blinded to study treatment. A designated limited number of sponsor colleagues within the study team will be unblinded to subject treatments in order to permit real-time interpretation of the safety and PK data; and provide information necessary to potentially alter the dose-escalation sequence. The study monitor will remain blinded to treatment until all monitoring for the study has been completed. Specimens from subjects randomized to placebo will not be routinely analyzed. To minimize the potential for bias, treatment randomization information will be kept confidential by Pfizer personnel and will not be released to the investigator or investigator site personnel until the study database has been locked. If an investigator would like to know the treatment assignment of a subject in the case of emergency or in the event of a safety concern, in which case, the process for breaking the blind must be followed.

The study will be double-blind (including site, investigator, subject), sponsor-open, for the Psoriasis cohorts. To minimize the potential for bias, treatment randomization information will be kept confidential and will not be released to the investigator or investigator site personnel until the study database has been locked. A designated limited number of Pfizer personnel will be unblinded to individual psoriasis subject treatment assignment to permit interpretation of interim analysis results, safety data, or management of subject's safety.

Site pharmacy staff involved in dose preparation will be unblinded. There may be one designated unblinded study monitor to perform drug accountability and site pharmacy monitoring activities.

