**3. INTERIM ANALYSES, FINAL ANALYSES AND UNBLINDING**

Safety and pharmacokinetic (PK) data will be reviewed after each study cohort and period.

This is a third party open study, with the investigator and subject blinded to study treatment. Specific Pfizer personnel (analytical staff, medical monitor, clinician, statistician, and pharmacokineticist) will be unblinded to subject treatments in order to permit real-time interpretation of the safety and pharmacokinetic data, and to provide information necessary to potentially alter the dose escalation sequence. To minimize the potential for bias, treatment randomization information will be kept confidential by Pfizer personnel and will not be released to the investigator/study staff until the conclusion of the study. Unblinding will not be performed until the final database has been locked for all cohorts. Final analysis will follow the official database release.

*An interim analysis of the change from baseline at Day 28 in PASI score (psoriasis key secondary endpoint) will be conducted for the first psoriasis cohort (400 mg dose cohort). The analysis will be performed when approximately 21 psoriasis subjects from the 400 mg cohort complete through study Day 28. Outcomes from this interim analysis may inform dose selection decisions/adjustments for later psoriasis subject cohorts to be enrolled in the study. The interim analysis is not planned to impact the conduct of the initial 400 mg psoriasis cohort. The analysis is planned to be performed after dosing of the full 400 mg psoriasis cohort (n=21 subjects completing through study Day 28). Any decisions or dose adjustments that are taken, will be applied to the subsequent psoriasis cohort. A designated limited number of Sponsor colleagues will review the interim analysis results to support any dose related decisions. For the healthy SAD/MAD cohorts, this is a sponsor-open study, and the sponsor may conduct unblinded reviews of the data during the course of the study for the purpose of safety assessment, facilitating dose-escalation decisions, facilitating PK/PD modeling, and/or to support clinical development. Unblinded results will be reviewed by a designated limited number of sponsor colleagues within the study team. A separate document containing the list of designated unblinded sponsor colleagues for the interim analysis will be prepared (see the Data Blinding Plan for further details) and saved in the SharePoint.*

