*The psoriasis multiple dose cohorts are double-blind with respect to investigator and subject. The psoriasis multiple dose cohorts will be sponsor-open (unblinded interim analysis results will be reviewed by a designated limited number of sponsor colleagues). In addition to the planned interim analysis from the 400 mg psoriasis cohort, the sponsor may analyze selected clinical endpoints at the end of the Psoriasis treatment period (Day 28) before the follow-up period is completed for all cohorts. For the purpose of safety assessment, select individuals from sponsor may conduct unblinded reviews of individual subject safety data if needed to*

*ensure proper management of subject safety. If needed, a designated limited number of sponsor colleagues may conduct unblinded reviews of the data during the course of the study to facilitate PK/PD modeling.*

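### SAP 9.3 settles two efficacy values in one visit window case by case, with no requirement that the choice be blind; a fixed rule would close this at no cost

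*SAP*

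**What the plan says.** SAP 9.3 sets windows of 3 days either side of each target day and states their scope: "Visit window (applicable for efficacy and PRO endpoints) will be assigned to the subjects in the Psoriasis cohorts". PASI is therefore covered. The Week 4 window, which supplies the Day 28 value, is Days 25-31. If a subject has more than one observation in a window, the assignment to a visit "will be done after the consultation with the study clinician and lead statistician". No order of preference, tie-break, blinding condition or record of the decision is specified. The footnote to the same table does give a mechanical fallback for a missing Day 1 baseline: the last available pre-dose value.

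On blinding, SAP 3 says: "Specific Pfizer personnel (analytical staff, medical monitor, clinician, statistician, and pharmacokineticist) will be unblinded to subject treatments". The stated purpose is "in order to permit real-time interpretation of the safety and pharmacokinetic data, and to provide information necessary to potentially alter the dose escalation sequence". SAP 3 and Protocol 9.7 make the psoriasis cohorts sponsor-open and plan an unblinded interim analysis of Day 28 PASI change in the 400 mg cohort. Protocol 5.2 adds: "A designated limited number of Pfizer personnel will be unblinded to individual psoriasis subject treatment assignment". SAP 3 does not list the people concerned for the interim: "A separate document containing the list of designated unblinded sponsor colleagues for the interim analysis will be prepared".

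**The concern.** The plan leaves the choice between two recorded efficacy values to judgement. The two roles consulted, clinician and statistician, also appear in the SAP's list of unblinded roles. If the people consulted know the treatment assignment, the choice can favour one arm, even without intent.

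The value most exposed is Day 28 PASI. It informs the dose of the second psoriasis cohort through the interim analysis, and it gives the final estimate of effect with its 90% confidence interval. The other post-baseline windows also feed the repeated measures model in SAP 9.2.1, so the gap is not confined to Week 4.

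SAP 3 also says that unblinding waits until the final database is locked for all cohorts. This gives no protection here. It cannot apply to the personnel whom the same paragraph has just described as unblinded, and the interim analysis takes place before that lock.

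**Working it through.** **1. The plan's own figure.** Protocol 9.1.2 gives 80.7% power for 14 subjects per arm, difference 7.8, SD 8 and one-sided 5% alpha. The SE of the difference is 8 × √(1/14 + 1/14) = 3.02, so the noncentrality is 7.8/3.02 = 2.58 on 26 degrees of freedom. A one-sided t test then has 80.69% power. The figure reproduces, is not in dispute, and does not depend on how duplicates are handled.

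**2. Who is consulted and who is unblinded.**
- Consulted (SAP 9.3): study clinician and lead statistician.
- Unblinded roles (SAP 3): these include clinician and statistician, for safety and PK review and dose escalation.
- Unblinded to individual psoriasis assignments (Protocol 5.2): a limited number of sponsor personnel, roles not given.
- Unblinded for the interim (SAP 3): people listed in a separate document that is not available here.

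The role names overlap. Whether the individuals overlap for the psoriasis cohorts cannot be settled from the documents. Nothing in SAP 9.3 excludes it.

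**3. Can Week 4 contain two values?** Subjects are housed through Day 28 (Protocol 3.1.2). The next outpatient visit named there is Day 35 ± 3, that is Days 32-38, which does not overlap Days 25-31. A second Week 4 value would have to come from an unplanned visit, from an early termination assessment on Days 29-31, or from a Day 29 assessment. The assessments listed for early withdrawal in Protocol 6.4 do not include PASI, and the PASI row of the psoriasis schedule cannot be read in the public text. Duplicates are therefore possible but should be rare.

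**4. Size if it happened.** Assume two exchangeable normal readings with independent errors of within-subject SD s. The expected value of the lower one is the mean minus s/√π, that is 0.564 × s. Neither s nor the share of subjects affected (f) is in the documents. The table takes f = 10% and assumes that the favourable reading is always chosen in one arm.

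| s (assumed) | Shift per affected subject | Shift in arm mean | As share of 7.8 | As share of SE, 14 v 7 | As share of SE, 14 v 14 |
|---|---|---|---|---|---|
| 2 | 0.564 × 2 = 1.13 | 0.11 | 1.4% | 3.0% | 3.7% |
| 4 | 0.564 × 4 = 2.26 | 0.23 | 2.9% | 6.1% | 7.5% |

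The SE for the interim (14 active, 7 placebo) is 8 × √(1/14 + 1/7) = 3.70.

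Two harsher cases:
- One affected placebo subject among the 7 at the interim moves the placebo mean by 1.13/7 = 0.16 to 2.26/7 = 0.32 points.
- If the lower value were always picked on active and the higher on placebo, the difference would shift by 2 × f × s/√π. For f = 5-20% and s = 1-3 points this is 0.06 to 0.68 points, or 0.7% to 8.7% of 7.8.

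**The case against.** The strongest reply is that unblinded selection has not been shown. SAP 9.3 speaks of consultation. It does not say when this happens, what the consultees see, or that they alone decide. The role list in SAP 3 is tied to safety, PK and dose escalation, which points to the healthy-subject cohorts. For the psoriasis reviews, Protocol 9.7 refers to a Data Blinding Plan and/or the SAP for who takes part and for steps to protect study integrity. That Data Blinding Plan may contain the missing safeguard. This stands: a reader might infer that the choice is made with values and assignments in view, and the documents do not support that as fact.

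A reader might also infer that the choice could never be audited. That does not follow. No record of the decision is required, but nothing suggests that the value not chosen is discarded, so both could be re-analysed.

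The reply on frequency and size stands too. Duplicates near Day 28 should be rare, and the shift is small against the sampling error. Investigator and subject are blinded, so the recorded scores themselves are not in question.

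What remains is the text of SAP 9.3: a discretionary choice of efficacy value with no blinding condition attached. None of these replies supplies one.

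**Conclusion.** The point holds as a minor weakness in a stated rule. SAP 9.3 permits a case-by-case choice between efficacy values and does not require it to be blind. Given the roles listed in SAP 3 and the sponsor-open psoriasis cohorts, unblinded selection is possible but not established.

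The likely effect is small: about 0.1 to 0.2 PASI points on an arm mean. This rests on three assumptions: 10% of subjects affected, a within-subject SD of 2 to 4 points, and the favourable value always chosen. The figure of 0.68 points needs 20% of subjects with duplicates and opposite selection in the two arms, which the visit schedule makes unlikely.

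It would be tempting to present this as inflated type I error. SAP 4.1 plans no hypothesis testing and PASI change is a secondary endpoint, so that reading does not fit. What could be affected is the estimate, its 90% confidence interval and the interim dose decision. The reason to act is that the route to bias can be removed for nothing, not that a large bias is expected.

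**What to change.** Replace the last sentence of SAP 9.3 with one mechanical rule for all post-baseline windows: use the scheduled-visit value if present; otherwise the observation closest to the target day; if two are equidistant, the earlier one; no case-by-case choice.

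Taking the earlier value also suits Week 4 without a special clause. Dosing ends on Day 28, so of two values equally far from that day the earlier falls within the treatment period.

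The cost is one sentence in the SAP. The rule needs no new data or visits and leaves the sample size and power unchanged (14 per arm, 80.7%).

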#### 9.4. Categorical Classes for ECG and Vital Signs of Potential Clinical Concern

##### Categories for QTcF

QTcF (ms)	450 ≤ max. <480	480 ≤ max. <500	max. ≥500
QTcF (ms) increase from baseline	30 ≤ max. <60	max. ≥60	

##### Categories for PR and QRS

PR (ms)	max. ≥300	
PR (ms) increase from baseline	Baseline >200 and max. ≥25% increase	Baseline ≤200 and max. ≥50% increase
QRS (ms)	max. ≥140	
QRS (ms) increase from baseline	≥50% increase	

##### Categories for Vital Signs

Systolic BP (mm Hg)	min. <90	
Systolic BP (mm Hg) change from baseline	max. decrease ≥30	max. increase ≥30
Diastolic BP (mm Hg)	min. <50	
Diastolic BP (mm Hg) change from baseline	max. decrease ≥20	max. increase ≥20
Supine pulse rate (bpm)	min. <40	max. >120
Standing pulse rate (bpm)	min. <40	max. >140

Measurements that fulfill these criteria are to be listed in report.

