In pivotal cardiovascular safety pharmacology and 1-month repeat-dose toxicity studies in cynomolgus monkeys, no PF-06826647-related changes were observed in any cardiovascular parameter measured up to the highest dose tested (300 mg/kg), corresponding to approximately 28x the projected human efficacious unbound  $C_{max}$ . In an exploratory cardiovascular safety pharmacology study in rats, PF-06826647-related increased diastolic and mean blood pressure (each +3 mmHg) from 0-2 hours postdose, and increased heart rate (+18 to +13 bpm) from 2-12 hours postdose, were observed at 500 mg/kg (the highest dose tested). No PF-06826647-related effects were observed in any parameter measured at  $\leq 50$  mg/kg, corresponding to 6.5x the predicted human efficacious unbound  $C_{max}$ .

The hERG  $IC_{50}$  for PF-06826647 was  $>10,000$  nM, which is  $>74x$  the predicted human efficacious unbound  $C_{max}$ .

PF-06826647 was negative for mutagenicity in the GLP bacterial reverse mutation assay. Although PF-06826647 was positive in the in vitro micronucleus assay in TK6 cells by an aneugenic mechanism, it did not induce micronuclei in vivo in reticulocytes in the 1-month study in rats (at exposures 41x the predicted human unbound efficacious  $C_{max}$  and  $AUC_{24}$ ).

PF-06826647 absorbs in the ultraviolet A (UVA) and ultraviolet B (UVB) range and could present potential risk for phototoxicity. Therefore, PF-06826647 will be evaluated for phototoxicity prior to enrollment in large clinical trials.

PF-06826647 was evaluated in rats and cynomolgus monkeys in single- and repeat-dose toxicity and/or toxicokinetic studies up to 1 month in duration. The high dose selection in the 1-month pivotal study was based on observed exposure plateau in exploratory studies. Target organs and systems identified with PF-06826647 administration in rats and monkeys include the immune and hemolymphatic systems (thymus, spleen, lymph nodes, bone marrow, erythron, and leukon), bone, and liver. In addition, other PF-06826647-related findings occurred in clinical observations, body weights, and/or clinical pathology parameters. In the immune and hemolymphatic system, decreased lymphoid cellularity within the lymphoid follicles of the thymus and spleen was observed in rats  $\geq 30$  mg/kg/day, and in the thymus,

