#### Laboratory, Vital Sign, and ECG Abnormalities:

Individual stopping rules will be based on repeated measures (single repeat preferably performed within 24 hours of initial result) of the parameters outlined below.

- Grade 3 lymphopenia ( $<500$  cells/mm^3).
- Grade 3 neutropenia ( $<1000$  cells/mm^3).
- Grade 3 ALT/AST ( $>5x$  upper limit of normal (ULN) when not accompanied by an increase in bilirubin).
- Grade 3 bilirubin ( $>2.0$  x ULN when not accompanied by an increase in ALT/AST).
- Changes in liver function tests that meet Hy's Law criteria.
- Serum creatinine  $\geq 1.5$  x ULN.

**Note:** An increase of  $\geq 0.3$  mg/dL (or  $\geq 26.5$   $\mu$ mol/L) in serum creatinine relative to subjects' own baseline measurement should trigger another assessment of SCr within 24-hours from awareness. See [Potential Cases of Acute Kidney Injury](#) for further guidance.

- Grade 2 Hemoglobin  $<10$  g/dL.
- Grade 2 Platelets  $<75,000$ /mm^3 or  $>750,000$ /mm^3.
- 12-lead ECG demonstrating QTc  $\geq 500$ ; or a QRS interval  $\geq 140$  msec or  $\geq 50\%$  increase from baseline; PR interval  $\geq 300$  msec or 25% increase over baseline when baseline  $>200$  msec.

Blood pressure or pulse rate measurements meeting criteria for individual stopping rules should be repeated at least twice, separated by at least 5 minutes, with the subject at rest, supine. If confirmed to be abnormal and confirmed to be clinically significant by investigator, dosing should be stopped and the blood pressure/pulse should be followed

periodically, as deemed appropriate by the investigator, until the blood pressure/pulse rate are returned to within normal limits or deemed acceptable by the investigator.

- Vital sign abnormalities:
  - Systolic blood pressure <90 mmHg or >160 mm Hg;
  - Diastolic blood pressure <50 mmHg or >100 mm Hg;
  - Pulse rate supine/sitting <36 or >120 beats per minute (bpm); standing <36 or >140 bpm.

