#### **4.2. Exclusion Criteria: Healthy Subject Single/Multiple Ascending Dose Cohorts**

Subjects presenting with any of the following characteristics/conditions will not be included in the study:

1. Evidence or history of clinically significant hematological, renal, endocrine, pulmonary, gastrointestinal, cardiovascular, hepatic, psychiatric, neurologic, or allergic disease (including drug allergies, but excluding untreated, asymptomatic, seasonal allergies at time of dosing).
2. Any condition possibly affecting drug absorption (eg, gastrectomy).
3. A positive urine drug screen.
4. History of regular alcohol consumption exceeding 7 drinks/week for females or 14 drinks/week for males (1 drink = 5 ounces (150 mL) of wine or 12 ounces (360 mL) of beer or 1.5 ounces (45 mL) of hard liquor) within 6 months of screening.
5. Treatment with an investigational drug within 30 days (or as determined by the local requirement) or 5 half-lives preceding the first dose of investigational product, whichever is longer.

6. Screening supine blood pressure  $\geq 140$  mm Hg (systolic) or  $\geq 90$  mm Hg (diastolic), following at least 5 minutes of supine rest. If blood pressure (BP) is  $\geq 140$  mm Hg (systolic) or  $\geq 90$  mm Hg (diastolic), the BP should be repeated two more times and the average of the three BP values should be used to determine the subject's eligibility.
7. 12-lead ECG demonstrating QTc  $> 450$ , or a QRS interval  $> 120$  msec at Screening. If QTc exceeds 450 msec, or QRS exceeds 120 msec, the ECG should be repeated two more times and the average of the three QTc (or QRS) values should be used to determine the subject's eligibility.
8. Subjects with **ANY** of the following abnormalities in clinical laboratory tests at screening, as assessed by the study-specific laboratory and confirmed by a single repeat, if deemed necessary:
  - Serum creatinine level above the upper limit of normal or an estimated Glomerular Filtration Rate (GFR) value  $\leq 80$  mL/min, based on the Cockcroft-Gault calculation, at Screening (see [Appendix 2](#)).
  - Aspartate aminotransferase (AST)/serum glutamic oxaloacetic transaminase (SGOT) or alanine aminotransferase (ALT)/serum glutamic pyruvic transaminase (SGPT)  $\geq$  values more than 1.5 times the upper limit of normal.
  - Fasting glucose  $> 110$  mg/dL.
  - Total bilirubin  $\geq 1.5$  x ULN.

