#### **8.4.6. Vital Signs Data**

Absolute values and changes from baseline in supine systolic and diastolic blood pressure and pulse rate will be summarized by cohort, treatment and time post-dose, according to sponsor reporting standards. Tables will be paged by parameter. Baseline is as defined in [Section 6.3.3](#).

Mean changes from baseline for supine systolic and diastolic blood pressure and pulse rate will be plotted against time post-dose. On each plot there will be separate line for each

treatment. Data from all cohorts will be plotted on the same figure using separate lines for different placebos. Corresponding individual plots of changes from baseline will also be produced for each cohort and treatment.

For supine systolic and diastolic blood pressure and pulse rate, the differences between each dose and placebo (dose – placebo) will be summarized (N, mean, 90% confidence interval) and plotted (mean) for each cohort, dose and timepoint (including baseline).

Maximum absolute values and changes from baseline for vital signs (for supine) will also be summarized descriptively by treatment. Numbers and percentages of subjects meeting the categorical criteria will be provided. All planned and unplanned post-dose timepoints will be counted in these categorical summaries. All values meeting the criteria of potential clinical concern will be listed.

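### SAP 9.4 has no upper absolute blood pressure limit, so a healthy subject who exceeds the Protocol 3.3 upper limit can be left out of the categorical counts and the listing of values of concern

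*SAP*

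**What the plan says.** Protocol 3.3 (Individual Stopping Rules for the Healthy Subjects) gives two-sided absolute limits: "Systolic blood pressure <90 mmHg or >160 mm Hg" and "Diastolic blood pressure <50 mmHg or >100 mm Hg". A reading outside them is to be repeated at least twice, and dosing stops only if the abnormality is confirmed and the investigator judges it clinically significant.

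SAP 9.4 (Categories for Vital Signs) has, for absolute pressure, a minimum below 90 systolic and below 50 diastolic. The rows for absolute blood pressure carry no upper limit. The change rows add a fall of the same size on each measure and, for rises, "max. increase ≥30" systolic and "max. increase ≥20" diastolic. The pulse rate rows of the same table have both a minimum and a maximum. The table closes with "Measurements that fulfill these criteria are to be listed in report".

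SAP 8.4.6 puts these categories to use: "Numbers and percentages of subjects meeting the categorical criteria will be provided", together with a listing of every value that meets them. It also plans summaries of absolute values and changes over time, a descriptive summary of maximum values and changes by treatment, and individual plots of change from baseline.

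Healthy subjects are excluded under Protocol 4.2 on: "Screening supine blood pressure $\geq 140$ mm Hg (systolic) or $\geq 90$ mm Hg (diastolic), following at least 5 minutes of supine rest". If the first reading is that high, the average of three decides. SAP Section 6 takes the last pre-dose value in each period as baseline, not the screening value. Vital signs are a primary safety endpoint in both documents.

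**The concern.** The two documents use different definitions of high blood pressure in healthy subjects. The protocol uses an absolute level. The SAP uses only a rise. The two agree when baseline is low and diverge when baseline is near the entry limit, because a modest rise then crosses the absolute level.

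This looks like an omission rather than a choice. SAP 9.4 otherwise captures every ECG and pulse limit in Protocol 3.3: QTc of 500 ms (as QTcF), PR of 300 ms, PR up 25% from a baseline above 200 ms, QRS of 140 ms, QRS up 50%, and pulse above 120 supine or 140 standing. Its lower pulse limit (40 against 36) is wider, so it still catches every protocol case. The upper blood pressure pair is the exception, and no reason is given.

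What is at stake is the completeness of one count and one listing for a primary safety measure. A reading over 160 or 100 that is not confirmed, or not judged clinically significant, does not stop dosing. Under Protocol 8.2.2, merely repeating an abnormal test does not make it an adverse event. The table and listing of values of concern are the natural place for such a reading to be counted and tied to a subject.

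**Working it through.** The plan states no figure on this point, so the check is whether the SAP categories cover the protocol limits.

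**Inputs.** Protocol 3.3 upper limits: systolic above 160, diastolic above 100. SAP 9.4 rises: at least 30 and at least 20. Protocol 4.2 entry: below 140 and below 90. Pressure is recorded to the nearest mmHg (Protocol 7.1.4), so whole numbers are used.

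**Condition for a missed reading.** Let b be the baseline and v the post-dose value. A systolic reading passes the protocol limit but meets no SAP category when v ≥ 161 and v − b ≤ 29. Such a v exists only if b ≥ 161 − 29 = 132, and the missed values then run from 161 to b + 29. For diastolic, v ≥ 101 and v − b ≤ 19 require b ≥ 101 − 19 = 82, and the missed values run from 101 to b + 19.

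| Measure | Baseline | Over the limit but unflagged | Rise |
|---|---|---|---|
| Systolic | 131 or lower | none | – |
| Systolic | 132 | 161 | 29 |
| Systolic | 135 | 161-164 | 26-29 |
| Systolic | 139 | 161-168 | 22-29 |
| Diastolic | 81 or lower | none | – |
| Diastolic | 82 | 101 | 19 |
| Diastolic | 85 | 101-104 | 16-19 |
| Diastolic | 89 | 101-108 | 12-19 |

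Two concrete cases: 138 to 162 systolic is a rise of 24, and 88 to 102 diastolic is a rise of 14. Neither is flagged.

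**Baselines above the entry limit.** The SAP baseline is the pre-dose value, and the notes to the MAD schedule let the investigator and sponsor decide whether a subject with out-of-range vital signs continues, unless an individual stopping rule is met. At a baseline of 150, readings of 161 to 150 + 29 = 179 go unflagged.

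**Other limits.**
- Pulse: below 36 implies below 40, and the upper limits are identical. No gap.
- Psoriasis (Protocol 3.4): the rules are rises above 30 systolic and above 20 diastolic. Any such rise meets the SAP's ≥30 or ≥20. No gap.

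**After adding max. >160 and max. >100.** Every v ≥ 161 or v ≥ 101 is flagged directly, so the missed set is empty at every baseline.

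**Weight of one subject.** With 6 active subjects per healthy cohort, one uncounted subject is 1/6 = 17% of a dose group in that table.

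**The case against.** The strongest reply is that SAP 9.4 is a reporting screen and Protocol 3.3 a stopping rule, and neither document says they must match. The SAP's own derived blood pressure endpoints (6.3.3) are maximum increase and decrease from baseline, and 9.4 follows that form. A high reading also appears elsewhere: in the summary of maximum absolute values, in the individual change plots, and possibly in general listings under sponsor standards that are not reproduced in the SAP. This stands in part. The reading is not lost, and the difference is not a contradiction. But a summary of maxima gives neither the number of subjects over the limit nor their identity, and the change plots do not show the absolute level.

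Three stronger readings are tempting, and the documents do not support them.
- A reader might infer that primary-endpoint data go missing. The primary endpoint is vital signs as a whole, not the 9.4 counts.
- A reader might set the 17% against the 50% dose-escalation rule in Protocol 3.2. Escalation is decided during the study, from unblinded review of emerging data and discussion with the investigator. End-of-study tables do not feed it.
- A reader might see the gap as hiding a known hazard, since Protocol 1.2.4 reports "PF-06826647-related increased diastolic and mean blood pressure (each +3 mmHg) from 0-2 hours postdose". That was an exploratory rat study at its highest dose, 500 mg/kg. The same section reports no effect at 50 mg/kg or below and no cardiovascular change in monkeys up to 300 mg/kg.

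Practical reach is also limited. Protocol 1.3.2 reports that, after six SAD and three MAD cohorts (53 healthy subjects), preliminary data indicated that the Section 3.3 stopping criteria had not been met. That does not exclude an isolated, unconfirmed reading.

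**Conclusion.** The point holds as a reporting gap confined to the healthy cohorts. If SAP 9.4 is followed as written, the 8.4.6 counts and the listing of values of potential clinical concern can omit a subject who exceeded a Protocol 3.3 upper limit. The affected baselines are systolic 132-139 and diastolic 82-89, and higher if the pre-dose value is above the screening limit. At 131/81 or lower the change criteria catch every case.

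The bands are worked out separately for each measure, so a subject missed on one may still be flagged on the other. The documents give no baseline distribution, so how many subjects would be affected cannot be estimated. The conclusion also assumes that the blank upper cells in the absolute blood pressure rows are blank in the source SAP. The pulse and change rows of the same table kept both entries, which makes a lost cell unlikely but not impossible. No treatment estimate, escalation decision or stopping action depends on this.

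**What to change.** In SAP 9.4, add max. >160 to the systolic row and max. >100 to the diastolic row, as reporting categories for the healthy SAD/MAD cohorts. These are the limits already in Protocol 3.3, so no clinical rule changes. The 8.4.6 counts and listing then cover both directions. The psoriasis cohorts need no change: their blood pressure rules are change-based and already covered. They may also enter at pressures up to just under 160/100 (Protocol 4.4), so absolute flags there would partly reflect baseline.

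The cost is two table cells and the matching output programming, with no extra data collection.
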